## 10.2 Analysis of Adverse Events

A treatment-emergent Adverse Event (TEAE) is defined as an adverse event with an onset date that is after the first dose of study drug, and no more than 30 days of the drug after the last dose of study drug.

Events where the onset date is the same as the study drug start date are assumed to be treatment-emergent, unless the study drug start time and the adverse event start time are collected and the adverse event start time is prior to the study drug start time. If an incomplete onset date was collected for an adverse event, the event will be assumed to be treatment-emergent unless there is other evidence that confirms that the event was not treatment-emergent (e.g., the event end date was prior to the study drug start date).

Adverse event data will be presented by SOCs and PTs using MedDRA version 19.0 or most up to date version. All adverse event tables will be sorted in alphabetical order by SOC and PT and descending percentages for each treatment group.

### 10.2.1 Analysis of Adverse Events for Period 1

#### 10.2.1.1 Adverse Events Overview

The number and percentage of subjects experiencing TEAEs will be summarized by "as treated" treatment group and overall for the following AE categories.

- All TEAEs
- Treatment-emergent serious adverse events (SAEs)
- Treatment-emergent severe adverse events
- TEAEs reasonably possibly related to study drug
- TEAEs of special interest
- TEAEs leading to discontinuation of study drug
- TEAE leading to death

In the AE overview summary, any event with an unknown severity will be considered as severe and any AE with an unknown relationship will be considered as having "reasonable possibility" of being related to study drug.

Additional AEs may be considered for tabulation/summary based on recommendations from Clinical and Safety as deemed appropriate.

For TEAEs of special interest, the point estimate and 95% CI (using normal approximation) will be provided for the treatment difference in AE percentage between each upadacitinib dose group and the combined placebo group.

As a sensitivity analysis, the AE overview summary will be repeated by randomized treatment groups (upadacitinib 15 mg QD, upadacitinib 30 mg QD and the combined placebo groups). In this summary, all AEs with an onset date after the first dose of study drug will be included, regardless of whether the AE occurred more than 30 days after the last dose of study drug.

#### **10.2.1.2 Adverse Events by System Organ Class and Preferred Term**

The number and percentage of subjects experiencing adverse events will be tabulated by SOC and MedDRA PT by "as treated" treatment group and overall. The SOCs will be presented in alphabetical order, and the PTs will be presented in alphabetical order within each SOC.

The following summaries of adverse events will be generated:

- All TEAEs
- Treatment-emergent serious adverse events (SAEs)
- Treatment-emergent severe adverse events
- TEAEs reasonably possibly related to study drug
- TEAEs leading to discontinuation of study drug
- TEAE leading to death
- Frequent AEs (reported in 2% of subjects or more in any treatment group)

Subjects reporting more than one adverse event for a given MedDRA preferred term will be counted only once for that term (most severe incident for the severity tables and most related incident for the relationship tables). Subjects reporting more than one type of adverse event within a SOC will be counted only once for that SOC. Subjects reporting more than one type of adverse event will be counted only once in the overall total.

As a sensitivity analysis, the AE summary by SOC and PT will be repeated by randomized treatment groups (upadacitinib 15 mg QD, upadacitinib 30 mg QD and the combined placebo groups). In this summary, all AEs with an onset date after the first dose of study drug will be included, regardless of whether the AE occurred more than 30 days after the last dose of study drug.

#### **10.2.1.3 TEAEs by Maximum Severity**

TEAEs will also be summarized by maximum severity by "as treated" treatment group and overall. If a subject has an AE with an unknown severity, then the subject will be counted in the severity category of unknown, even if the subject has another occurrence of the same event with a severity present. The only exception is that if the subject has another occurrence of the same AE with the most extreme severity – severe. In this case, the subject will be counted under the severe category.

#### **10.2.1.4 TEAEs by Relationship**

TEAEs will also be summarized by relationship to upadacitinib and Placebo, as assessed by the investigator, by "as treated" treatment group and overall. If a subject has a TEAE with an unknown relationship, then the subject will be counted in the relationship category of "unknown," even if the subject has another occurrence of the same event with a relationship present. The only exception is if the subject has another occurrence of the same TEAE with a relationship assessment of "reasonable possibility." In this case, the subject will be counted under the "reasonable possibility" category.

### 10.2.1.5 Frequent ( $\geq 2\%$ ) Adverse Events and Reasonably Possibly Related Adverse Events by System Organ Class and Preferred Term

TEAEs and reasonably possibly related AEs occurring for more than 2% of the subjects in any of the "as treated" treatment groups will be summarized by MedDRA PT in decreasing frequency separately.

### 10.2.1.6 Adverse Events of Special Interest

The Adverse Events of Special Interest (AESI) categories will be summarized and presented by "as treated" treatment group and overall using SOC and MedDRA PT. The AESI categories will be identified per Standard MedDRA Queries (SMQs)/Company MedDRA Queries (CMQs). Adjudicated cardiovascular events will be summarized and presented by treatment group using the CAC adjudicated categories.

**Table 8. AESI for Upadacitinib with SMQs/CMQs/PTs Searches**

AESI	Type of MedDRA Query	Broad or Narrow Search	SMQ/CMQ Search Criteria
Serious Infections	CMQ		"Infections" – Subset for SAEs
Opportunistic Infection excluding Tuberculosis and Herpes Zoster	CMQ		"Opportunistic Infection excluding Tuberculosis and Herpes Zoster"
Possible Malignancy	SMQ	Narrow	"Malignancies"
Malignancy	SMQ		"Malignant tumours"
Non-Melanoma Skin Cancer (NMSC)	SMQ	Narrow	Skin Malignant tumours (Narrow SMQ) removing Melanoma CMQ
Malignancy excluding NMSC			"Malignant tumours" SMQ removing NMSC output
Lymphoma	SMQ		"Malignant Lymphomas"
Hepatic Disorder	SMQ	Narrow	"Drug Related Hepatic Disorders"
Adjudicated Gastrointestinal Perforations	Output from adjudication		
Anemia	CMQ		"Non-Hemolytic and Non-Aplastic Anemias"

**Table 8. AESI for Upadacitinib with SMQs/CMQs/PTs Searches (Continued)**

AESI	Type of MedDRA Query	Broad or Narrow Search	SMQ/CMQ Search Criteria
Neutropenia	CMQ		"Hematological Toxicity – Neutropenia"
Lymphopenia	CMQ		"Hematological Toxicity – Lymphopenia"
Herpes Zoster	CMQ		"Herpes Zoster"
Creatine Phosphokinase (CPK) Elevation	PT		Search only for the PT of "Blood creatine phosphokinase increased"
Renal Dysfunction	SMQ	Narrow	"Acute Renal, Failure"
Active Tuberculosis	CMQ		"Active Tuberculosis"
Adjudicated Cardiovascular Events	Output from CAC		
MACE*			
Cardiovascular Death			
Non-fatal Myocardial Infarction			
Non-fatal Stroke			
Undetermined/Unknown Cause of Deaths			
Other Cardiovascular events			
Adjudicated Thrombotic Events	Output From CAC		
Venous Thromboembolic Events**			
Deep Vein Thrombosis			
Pulmonary Embolism			
Other Venous Thrombosis			
Arterial Thromboembolic Events (non-cardiac, non-neurologic)			

CAC = Cardiovascular Adjudication Committee; CMQ = company MedDRA query; PT = preferred term; SMQ = standard MedDRA query

\* MACE; Major Adverse Cardiovascular Events, defined as cardiovascular death, non-fatal myocardial infarction and non-fatal stroke.

\*\* Venous thromboembolic events (VTE) include deep vein thrombosis (DVT) and pulmonary embolism (PE) (fatal and non-fatal).

Additional AEs may be considered for tabulation/summary based on recommendations from Clinical and Safety as deemed appropriate.

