6.1.1.3 Adverse Events of Special Interest

The following AEs of special interest will be monitored during the study (see detailed toxicity management in Section [6.1.7](#)):

- Serious infections;
- Opportunistic infections;
- Herpes zoster;
- Active tuberculosis;
- Malignancy (all types);
- Adjudicated Gastrointestinal perforations;

- Adjudicated cardiovascular events (e.g., major adverse cardiovascular event [MACE]);
- Anemia;
- Neutropenia;
- Lymphopenia;
- Increased serum creatinine and renal dysfunction;
- Hepatic events and increased hepatic transaminases;
- Increased creatine phosphokinase (CPK);
- Adjudicated embolic and thrombotic events (non-cardiac, non-CNS).

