Serum Creatinine	
 • If serum creatinine is > 1.5 × the baseline value and > ULN, repeat the test for serum creatinine (with subject in an euvoletic state) to confirm the results. If the results of the repeat testing still meet this criterion, then interrupt study drug and re-start study drug once serum creatinine returns to ≤ 1.5 × baseline value and ≤ ULN. • If confirmed serum creatinine ≥ 2 mg/dL, interrupt study drug and re-start study drug once serum creatinine returns to normal reference range or its baseline value. 
For the above serum creatinine elevation scenarios, complete supplemental renal eCRF.

Table 7. Specific Toxicity Management Guidelines for Abnormal Laboratory Values (Continued)

Laboratory Parameter	Toxicity Management Guideline
Creatine Phosphokinase	
 • If confirmed CPK value $\geq 4 \times$ ULN and there are no symptoms suggestive of myositis or rhabdomyolysis, the subjects may continue study drug at the investigator's discretion. • If CPK $\geq 4 \times$ ULN accompanied by symptoms suggestive of myositis or rhabdomyolysis, interrupt study drug and contact AbbVie TA MD. 
For the above CPK elevation scenarios, complete supplemental CPK eCRF.

For allowed study drug interruption, the following rules apply:

Period 1

- Allow study drug interruption up to 7 consecutive days for AEs and emergency surgery. Elective surgery will not be allowed during this 12 week-period.
- If the subject must undergo emergency surgery, the study drug should be interrupted at the time of the surgery. After emergency surgery, allow reintroduction of study drug once the physician has examined the surgical site and determined that it has healed and there is no sign of infection.

Period 2

- Allow study drug interruption up to 7 consecutive days for AEs and emergency surgery up until the Week 24 visit in Period 2, and after Week 24 and thereafter, up to 30 consecutive days of study drug interruption is allowed. The Investigator will make determination if study drug should be restarted for interruptions > 30 days.
- Elective surgery is allowed starting at Week 24 in Period 2. If the subject undergoes elective surgery, the study drug should be interrupted 1 week prior to the planned surgery. Allow reintroduction of study drug once the physician has examined the surgical site and determined that it has healed and there is no sign of infection.

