8.1.5.2.1 Treatment-Emergent Adverse Events (TEAE)

AEs will be coded using MedDRA. A TEAE is defined as AE that began or worsened in severity after initiation of study drug.

AEs starting more than 30 days following the last dose of study drug will not be included in summaries of TEAEs. For subjects who continued into Period 2, AEs that are reported in Period 2 will be captured in the combined safety analysis of Period 1 and Period 2.

As a general safety summary, the number and percentage of subjects experiencing TEAEs will be summarized for each treatment group for the following AE categories:

- All AEs;
- All severe AEs;
- All reasonably possibly related AEs;
- All SAEs;
- Frequent AEs (reported in 2% of subjects or more in any treatment group);
- Frequent reasonably possibly related AEs (reported in 2% of subjects or more in any treatment group);
- Discontinuations due to AEs;
- Death.

Additional AEs may be considered for tabulation/summary based on recommendations from Clinical and Safety as deemed appropriate.

TEAEs will be summarized and presented by system organ classes (SOCs) and preferred terms (PTs) using MedDRA. The SOCs will be presented in alphabetical order, and the PTs will be presented in alphabetical order within each SOC.

TEAE will also be summarized by maximum severity and by maximum relationship.

The AEs of special interest (including but not limited to serious infection, opportunistic infection, herpes zoster, TB, gastrointestinal perforations, malignancies, MACE, renal dysfunction, anemia, increased CPK, non-cardiac, non-CNS embolic and thrombotic events, and drug-related hepatic disorders) will be summarized. Event rate (per 100 patient years) for AEs of special interest will also be summarized for the combined safety analysis of Period 1 and Period 2.

All AEs leading to discontinuation of study drug will be presented in listing format. A listing by treatment group of TEAEs grouped by SOC and MedDRA preferred term with subject identification numbers will be generated.

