#### **10.3.2.3 Assessment of Potentially Clinical Significant Laboratory Variables**

The criteria for potentially clinically significant laboratory values will be determined by OMERACT criteria of Grade 3 or 4. For creatine phosphokinase and creatinine, NCI CTC criteria will be used.

The number and percentage of subjects meeting the criteria for potentially clinically significant laboratory values will be summarized by "as treated" treatment group and overall. Comparisons of the percentage of subjects experiencing a value meeting the criteria between treatment groups will be performed using Fisher's exact tests. Only p-values  $\leq 0.100$  when rounded to three digits will be presented.

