L7. Hyponatraemia (mmol/l)***	-	125 – 129	120 – 124	< 120
L8. Hypokalaemia (mg/dl)***	-	3.0 – 3.4	2.5 – 2.9	< 2.5
L9. CPK (also if polymyositis-disease)****	1.2 – 1.9 × ULN	2.0 – 4.0 × ULN	4.0 × ULN with weakness but without life-threatening signs or symptoms	> 4.0 × ULN with signs or symptoms of rhabdomyolysis or life-threatening
L10. Serum uric acid	1.2 – 1.6 × ULN	1.7 – 2.9 × ULN	3.0 – 5.0 × ULN or gout	NA
L11. Creatinine (mg/dl)****	1.1 – 1.3 × ULN	1.4* – 1.8 × ULN	1.9 – 3.0 × ULN	> 3.0 × ULN
L12. SGOT (AST)	1.2 – 1.5 × ULN	1.6 – 3.0 × ULN	3.1 – 8.0 × ULN	> 8.0 × ULN
L13. SGPT (ALT)	1.2 – 1.5 × ULN	1.6 – 3.0 × ULN	3.0 – 8.0 × ULN	> 8.0 × ULN
L14. Alkaline phosphatase	1.1 – 1.5** × ULN	1.6 – 3.0 × ULN	3.0 – 5.0 × ULN	> 5.0 × ULN
L15. T. bilirubin	1.1 – 1.4 × ULN	1.5 – 1.9 × ULN	2.0 – 3.0 × ULN	> 3.0 × ULN
L16. LDH	1.3 – 2.4 × ULN	2.5 – 5.0 × ULN	5.1 – 10 × ULN	> 10 × ULN

M. Urinalysis				
M1. Haematuria	Micro only	Gross, no clots	Clots, transfusion < 2 units	Transfusion required
M2. Proteinuria (per 24 h)	300 – 500 mg (tr/1+)	501 – 1999 mg (2+)	2 – 5.0 g (3+) nephrotic syndrome	5.0 g (4+) anasarca
M3. WBC in urine	NA	NA	Indicating acute interstitial nephritis	Associated with acute renal failure
M4. Uric acid crystals	Present without symptoms	NA	With stones or symptoms of stones (e.g., renal colic)	Causing renal outflow obstruction and hospitalization

\*: in L11, 1.5 – 1.8 × ULN is changed to 1.4 – 1.8 × ULN.

\*\* : in L14, 1.1 – 2.0 × ULN is changed to 1.1 – 1.5 × ULN.

\*\*\*: in L3, L7 and L8, mg/dl is changed to mmol/l.

\*\*\*\*: For CPK and Creatinine NCI CTC grading will be used. For CPK therefore the following gradings apply: Grade 1: > ULN – 2.5 × ULN; Grade 2: > 2.5 – 5.0 × ULN; Grade 3: > 5.0 – 10.0 × ULN; Grade 4: > 10.0 × ULN; For Creatinine the following gradings apply: Grade 1: > 1 – 1.5 × Baseline; > ULN – 1.5 × ULN; Grade 2: > 1.5 – 3.0 × Baseline; > 1.5 – 3.0 × ULN; Grade 3: > 3.0 baseline; > 3.0 – 6.0 × ULN; Grade 4: > 6.0 × ULN

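### Creatinine rises that require study drug interruption but stay at Grade 2 appear in no long-term abnormal-laboratory count, listing or shift table, and SAP Table 8 has no creatinine term

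*SAP*

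**What the plan says.** **Protocol.** Section 6.1.1.3 lists "Increased serum creatinine and renal dysfunction" among the adverse events of special interest (AESIs). The statistical section, 8.1.5.2.1, gives an open-ended list with the shorter wording "MACE, renal dysfunction, anemia, increased CPK". Table 7 in Section 6.1.7 has two creatinine rules. The first reads "If serum creatinine is > 1.5 × the baseline value and > ULN, repeat the test for serum creatinine", with interruption if the repeat confirms it. The second reads "If confirmed serum creatinine ≥ 2 mg/dL, interrupt study drug". Both call for a supplemental renal eCRF.

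Protocol 8.1.5.1 plans safety analyses for Period 1 alone and for Periods 1 and 2 combined, and says that laboratory shifts are tabulated. Protocol 8.1.5.3 describes shift tables by grade without limiting them to Period 1.

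**SAP.** The renal row of Table 8 is a narrow standard query, "Acute Renal, Failure". No row names creatinine. CPK, by contrast, has a preferred-term search of its own. For laboratory values, Section 10.3.2.3 states: "The criteria for potentially clinically significant laboratory values will be determined by OMERACT criteria of Grade 3 or 4". Creatinine is graded by NCI CTC instead, and Appendix A gives "Grade 3: > 3.0 baseline; > 3.0 – 6.0 × ULN; Grade 4: > 6.0 × ULN". Grade 2 is above 1.5 and up to 3.0 times baseline or ULN. Section 10.3.3.2 applies the Grade 3–4 criterion to the long-term count and listing. Shift tables are in 10.3.2.2, under the Period 1 heading, and 10.3.3 has none.

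**The concern.** The protocol treats a confirmed creatinine rise as serious enough to interrupt dosing and fill in a dedicated form. The long-term laboratory outputs nevertheless start at a higher grade than that rule. A subject interrupted for a rise to twice baseline would not be in the long-term abnormal-laboratory count, its listing or a shift table.

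The adverse event route is uncertain. Under protocol 6.1.1.1 a laboratory abnormality is an adverse event only if it leads to discontinuation from the study, needs therapeutic intervention, or is judged one by the investigator. Interruption of study drug is not on that list. The SAP names no analysis of the renal eCRF.

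At stake is whether the long-term safety report can say how often creatinine rose far enough to interrupt treatment in each exposure group. That is a descriptive safety question. Period 1 efficacy is not affected.

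**Working it through.** No planned figure needs reproducing. The check compares thresholds.

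**1. First Table 7 rule against the Grade 3 cut-off.** Work in multiples of ULN and let b = baseline/ULN.
- Interruption applies above max(1.5b, 1).
- Grade 3 starts above min(3b, 3). This reads the semicolon in Appendix A between the baseline and ULN criteria as *or*.
- The uncounted band lies between the two.

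| b | Interruption above (× ULN) | Grade 3 above (× ULN) | Band (× baseline) |
|---|---|---|---|
| 0.5 | 1.0 | 1.5 | 2.0 to 3.0 |
| 0.667 | 1.0 | 2.0 | 1.5 to 3.0 |
| 0.8 | 1.2 | 2.4 | 1.5 to 3.0 |
| 1.0 | 1.5 | 3.0 | 1.5 to 3.0 |
| 1.2 | 1.8 | 3.0 | 1.5 to 2.5 |

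If the semicolon means *and*, Grade 3 starts above max(3b, 3). At b = 0.8 that is max(2.4, 3) = 3.0, and the band widens to 1.2–3.0 × ULN.

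**2. Second Table 7 rule (2 mg/dL).** The documents give no creatinine ULN, so assume 0.9 to 1.3 mg/dL. Then 2/0.9 = 2.22 and 2/1.3 = 1.54 × ULN, both Grade 2 on the ULN criterion. A value of 2 mg/dL exceeds 3 × baseline only if baseline is below 2/3 = 0.667 mg/dL.

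**3. Example.** Assume ULN 1.1 and baseline 0.8 mg/dL.
- 1.6 mg/dL is 1.6/0.8 = 2.0 × baseline: interruption if confirmed, Grade 2, not counted.
- 2.2 mg/dL is 2.2/0.8 = 2.75 × baseline: interruption if confirmed, Grade 2, not counted.
- 2.5 mg/dL is 2.5/0.8 = 3.1 × baseline: interruption if confirmed, Grade 3, counted and listed.

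**4. Is creatinine the exception?** Set Table 7 beside Appendix A. The interruption thresholds for hemoglobin (below 8 g/dL, or a fall of at least 3.0), neutrophils (below 1000), lymphocytes (below 500), white cells (below 2000), platelets (below 50,000) and ALT/AST (all rules above 3 × ULN) fall essentially in Grades 3–4. They therefore reach the long-term count. Symptomatic CPK from 4 to 5 × ULN is also Grade 2, but CPK has its own AESI row. Liver tests have a separate long-term table (SAP 10.3.3.3). Creatinine has neither.

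**5. Other long-term outputs.** All values enter the mean-change summary (SAP 10.3.3.1), where a few large rises can be hidden by the average. Rises recorded as adverse events enter the rates by preferred term (SAP 10.2.2.2). Neither gives the number of subjects in the band.

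**The case against.** The other side has five fair points.

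- **The SAP follows the protocol's statistical section.** Section 8.1.5.2.1 names renal dysfunction and increased CPK but not creatinine, and Table 8 does the same. This weakens the CPK contrast as evidence of a slip in the SAP. The protocol differs from itself, so all three places need reconciling. The list in 8.1.5.2.1 is open-ended, however, and does not remove creatinine from 6.1.1.3.
- **The shift tables are planned at protocol level.** That is true. The defect is that SAP 10.3.3 does not carry them into the long-term analysis.
- **A creatinine row in Table 8 would largely repeat a rate already reported by preferred term.** This stands for the AESI part of the fix. It would also miss rises never recorded as adverse events, so the laboratory table matters more.
- **The terms inside the narrow query are not in the documents.** A rise reported as acute renal failure would be counted, and the SAP allows extra tabulations. What the query leaves out cannot be proved here. An option to tabulate more is still not a planned analysis.
- **The outputs are descriptive.** This limits the weight of the point but does not remove it.

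A reader might go further and infer that every creatinine rise forcing an interruption is missing from the long-term counts. The documents do not support that: rises above 3 × baseline or 3 × ULN also trigger interruption and are both counted and listed. A reader might also infer that the long-term renal signal is understated by some factor. The documents give no incidence for either kind of event. The AESI rate also counts events, repeats included, so it cannot be set against a number of subjects with laboratory rises.

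**Conclusion.** The point holds for Grade 2 creatinine. Rises of about 1.5 to 3 times baseline or ULN that meet a Table 7 interruption rule appear in no planned long-term abnormal-laboratory count, listing or shift table. They reach the long-term adverse event rates only if recorded as adverse events. Separately, protocol 6.1.1.3, protocol 8.1.5.2.1 and SAP Table 8 do not describe the renal AESI in the same way.

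The size can be stated as a band, such as 1.2 to 2.4 × ULN for a baseline of 0.8 × ULN. It cannot be stated as a number of subjects or a rate. The first-rule band rests on reading the two Appendix A criteria as alternatives, and the other reading makes it wider for baselines below ULN. The 2 mg/dL result rests on the assumed ULN of 0.9 to 1.3 mg/dL.

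This should be fixed, because the change is small and can still be made: SAP 11.1 says that version 3.0 governs only future long-term reporting.

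**What to change.** **SAP 10.3.3.** Add one of the following, by the exposure groups of SAP 8.1:
- the long-term shift table by grade that the protocol plans; or
- the number of subjects, with an exposure-adjusted rate, who have creatinine of Grade 2 or higher or who meet the existing Table 7 criteria.

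If the Appendix A criteria are alternatives, a Grade 2 cut-off captures every value under the first rule, and every value of 2 mg/dL or more for the assumed ULN range. It is also wider than the first rule: at b = 0.5 it starts above 1.5 × 0.5 = 0.75 × ULN, while the rule needs a value above ULN. A count on the Table 7 criteria is closer to the protocol's action point and does not depend on how the semicolon is read. The SAP should state whether confirmation is required and which baseline applies, since 10.3.3.2 resets baseline for subjects switched from placebo.

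**Renal AESI.** Reconcile protocol 6.1.1.3, protocol 8.1.5.2.1 and SAP Table 8, for example with a creatinine preferred-term row as for CPK.

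**Cost.** SAP wording, one extra table, a wording correction across the two documents, and possibly a less favourable renal safety summary. No new data are needed, Period 1 is not reopened, and no change to the interruption rules is proposed.
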